where $\lambda_{finerenone,k}$ denotes the hazard rate of the finerenone treatment group in stratum k and $\lambda_{placebo,k}$ denotes the hazard rate of the placebo treatment group in stratum k . In this context, the hazard rate is defined as the instantaneous risk of a primary composite event at a given time point provided that no such event has yet taken place. The test statistic of the stratified logrank test compares the observed number of events with the number of events expected under the null hypothesis H_0 in each treatment group per stratum.

The following decision rule to test the null hypothesis will be applied. According to the size of this study and the expected number of events, it is justified to assume under H_0 a sufficiently close approximation of the logrank test (see reference 4) to the normal distribution. If the logrank test statistic (i.e. the standardized difference of the observed number of events and expected number of events stratified by the stratification factors region, type of albuminuria, eGFR category and history of CVD) is larger than the critical quantile from the normal distribution, the null hypothesis will be rejected in favor of the alternative hypothesis.

The nominal significance levels and the critical values at the final analysis will be adjusted to account for the interim analysis, see section 4.7 for more details.

In order to provide a point estimate of the hazard ratio and a corresponding two-sided 95% confidence interval, a stratified Cox proportional hazard regression model will be used. The stratification variables will be included in the STRATA statement in SAS PROC PHREG, which will assume proportional hazards for each level of one particular stratification factor.

Kaplan Meier curves will be provided for the cumulative incidence risk of outcome events by treatment groups.

To derive the logrank test statistic and the corresponding p-value, SAS program code corresponding to the following will be used:

```
PROC LIFETEST DATA = <dataset> ALPHA=0.05 METHOD=KM;
  TIME ttevalue * ttecnsr(1);
  STRATA {stratumn} / GROUP=trtgrpnr TEST=(logrank);
RUN;

/*
where
dataset = name of sub-dataset including all ITT subjects
randomized
trtgrpnr = variable coding randomized treatment group
ttevalue = time to first occurrence of primary efficacy
outcome event
ttecnsr = censoring index (1 = right-censored, 0 = event)
stratumn = variables for stratification factors
*/
```

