6.2.1.2 Primary efficacy variable: supportive analysis

The primary analysis of the primary efficacy variable will be repeated in the PPS as a supportive analysis. For the PPS analysis, the censoring rules for the primary analysis specified in Section 6.2.1.1 will be further restricted to events occurring up to 30 days after last study drug intake.

Accordingly, subjects with censoring or event date more than 30 days after last study drug intake in the primary analysis will be censored at the date of last study drug intake +30 days.

The following supportive analyses of the primary efficacy variable will be performed in the FAS and PPS unless specified otherwise.

The originally planned presentation of absolute and relative frequency of subjects with an event of the primary composite endpoint will be superseded by the Kaplan-Meier estimates described below.

Cumulative incidence probabilities for each treatment group based on Kaplan-Meier estimates for the time to the first primary composite endpoint event and their differences between finerenone and placebo will be derived at appropriate time points along with 95% confidence

intervals (CIs) and Number Needed to Treat (NNT). The CIs will be calculated based on a normal approximation and using the Greenwood formula for the standard deviation [4], and the NNT will be calculated as the inverse difference of the Kaplan-Meier estimates between finerenone and placebo for the selected time points. In addition, corresponding Kaplan-Meier curves showing cumulative incidence probabilities will be presented for each treatment group. These analyses will be presented in total and for each level of the stratification factors.

For the primary composite endpoint and the individual events, the incidence rate per 100 patient-years will be presented by treatment group, which is defined as the number of subjects with an event divided by the time a patient is at risk for the respective event, i.e. either the time from randomization until the first event or the censoring time, multiplied by 365.25*100. Kaplan-Meier plots, logrank tests and Cox proportional hazards regression for the time to first event of the individual components will also be provided as part of exploratory efficacy (see section 6.2.3).

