An ‘on-treatment’ analysis will also be performed, repeating the Kaplan Meier estimates and curves as well as the inferential statistics (stratified logrank test and stratified Cox regression model) on the FAS. For the on-treatment analysis, as described for the PPS analysis above, the censoring rules for the primary analysis will be adapted by further restricting to events occurring up to 30 days after last study drug intake.

The logrank test as well as the Cox regression model will also be performed without including stratification factors. The plausibility of the proportional hazards assumption will be assessed by visually examining the plot of the log of the negative log of Kaplan-Meier estimates of the survival function versus log time for evidence of non-parallelism, and by including a treatment by log-transformed time interaction into the Cox model. For the latter, the SAS code is adapted as follows:

```
PROC PHREG DATA = <dataset>;
  MODEL ttevalue * ttecnsr(1) = trtgrpnr trtltime / RL
  TIES=EFRON ALPHA=0.05;
  STRATA {stratum};
  trtltime = trtgrpnr*log(ttevalue);
RUN;
```

The significance of the interaction will be tested at the 5% type I error level. If the interaction is significant and there is strong evidence of non-proportionality from the plots, time-dependent hazard ratios will be estimated with the model that includes the interaction term.

The censoring mechanism of subjects without an event of the primary composite endpoint at the time of analysis is assumed to be non-informative for the primary efficacy analysis. This also implies that the primary analysis is valid under a missing at random (MAR) assumption. Sensitivity analyses will be performed, assessing the impact of a potential informative censoring of subjects lost to follow-up or with withdrawn consent. Non-CV deaths will be treated as censored observations as in the primary analysis.

A summary of the amount of missing data by treatment arm will be given, including number of subjects who have incomplete follow-up on the respective endpoint as well as the ratio of the observed follow-up time to the expected follow-up time for the respective endpoint.

Robustness with respect to missing data will be investigated with a tipping point analysis on the FAS (based on the ITT approach). The analysis will:

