6.2.2 Analysis of secondary efficacy variables

6.2.2.1 Secondary efficacy variables: primary analysis

Secondary efficacy variables are as follows:

- Time to first occurrence of the following renal composite endpoint:
 - onset of kidney failure, a sustained decrease of eGFR $\geq 40\%$ from baseline over at least 4 weeks, or renal death
- Time to all-cause hospitalization
- Time to all-cause mortality
- Change in UACR from baseline to Month 4
- Time to first occurrence of the following renal composite endpoint: onset of kidney failure, a sustained decrease in eGFR of $\geq 57\%$ from baseline over at least 4 weeks or renal death.

The primary analysis of the secondary efficacy variables will be conducted in the FAS.

See section 4.7 for the testing hierarchy for secondary endpoints and for multiplicity adjustment of significance levels.

The primary analysis of the secondary time-to-event endpoints will be conducted analogously to the primary analysis of the primary composite endpoint, with modifications to the

censoring rules as the events will differ. In the event of premature termination from the study with no subsequent follow-up information, subjects without any information about the composite endpoint after baseline will be censored at Day 1, and the following censoring rules will also apply:

- Renal events will be counted up to the day of the last visit when complete information on all components of the composite renal endpoint is available with an additional rule for events occurring after this visit. To account for events of kidney failure or renal death after the last eGFR is recorded at a clinic visit, such events will be included in the efficacy analysis if they occur in the period up to one day before the next planned clinic visit. This period would be a maximum of 5 months, given the next scheduled clinic visit should take place 4 months later, plus a time window for late attendance of one month. In addition, should the subject have a non-renal death in this period then the date of death will be used as the censoring date. Randomized subjects without an event of the renal composite endpoint at the time of analysis will be censored at the date of their last visit when complete information on all components of the composite renal endpoint is available, up to and including the EOS visit (should this visit satisfy this rule), or date of non-renal death using a time window of 5 months as above if a subsequent clinic visit had been planned.

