- Hospitalization events will be counted up to the day of withdrawal from the study or death. Randomized subjects without a hospitalization event at the time of analysis will be censored at the date of their last contact up to and including the EOS visit or date of death.
- All-cause mortality will be counted up to the last date vital status could be obtained. Randomized subjects without such an event at the time of analysis will be censored at the last date vital status could be obtained up to and including the EOS visit.

An ANCOVA model will be fitted to the logarithmized ratios of UACR at Month 4 to UACR at baseline including the factors treatment group, the stratification factors region, type of albuminuria, eGFR category and history of CVD and the logarithmized baseline UACR as covariate. Corresponding two-sided 95% confidence intervals will be computed. As the baseline UACR defines the type of albuminuria, the log-transformed baseline UACR will be nested as covariate in type of albuminuria.

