6.2.2.2 Secondary efficacy variables: supportive analysis

The primary analysis of the secondary efficacy time-to-event endpoints will be repeated in the PPS as a supportive analysis. For the PPS analysis, the censoring rules for the primary analysis specified in Section 6.2.2.1 will be further restricted to events occurring up to 30 days after last study drug intake.

Accordingly, subjects with censoring or event date more than 30 days after last study drug intake in the primary analysis will be censored at the date of last study drug intake +30 days.

Subjects with no event up to 30 days after treatment discontinuation will be censored at the date of treatment discontinuation +30 days. For the secondary renal composite endpoints subjects with no event up to 30 days after treatment discontinuation will be censored at the date of their last visit when complete information on all components of the composite renal

endpoint is available, or the date of non-renal death, if this occurred up to 30 days after treatment discontinuation and within 5 months after the last visit with complete information on all components of the composite renal endpoint.

The supportive analyses of the secondary time-to-event endpoints will correspond to those done for the primary composite endpoint in the FAS and PPS (see section 6.2.1.2), except for the tipping point analysis which will only be performed for the key secondary endpoint based on the FAS.

All-cause hospitalization (and sub-categories “CV hospitalization” and “Heart failure hospitalization”) will be further analyzed considering recurrent events by means of the following methods:

- Cumulative incidences based on the Mean Cumulative Function (MCF) to account for recurrent events as described by Doganaksoy and Nelson (1998) [10]
- Andersen-Gill model for first and recurrent events with robust standard errors (identical with Lin Wei Yang and Ying proportional rates model) to test the null hypothesis of the rate ratio for finerenone vs. placebo being equal to 1 [11,12]

Censoring for the recurrent event analysis of hospitalization events will follow the rules as outlined for the time to the first hospitalization event (at the last contact date or date of death and up to the EOS visit).

UACR at Month 4 in the PPS will be analyzed using an ANCOVA as described above. In addition, the following sensitivity analyses accounting for missing data at Month 4 will be conducted:

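### Efficacy cumulative incidence and NNT are one minus Kaplan-Meier with competing deaths censored, so absolute risks are overstated; Aalen-Johansen is planned only for hyperkalaemia and potassium

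*SAP*

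**What the plan says.** SAP 6.2.1.1 describes the main curves this way: "Kaplan Meier curves will be provided for the cumulative incidence risk of outcome events by treatment groups". SAP 6.2.1.2 then plans "Cumulative incidence probabilities for each treatment group based on Kaplan-Meier estimates for the time to the first primary composite endpoint event", together with differences between arms. On precision it says "The CIs will be calculated based on a normal approximation and using the Greenwood formula for the standard deviation", and on NNT "NNT will be calculated as the inverse difference of the Kaplan-Meier estimates between finerenone and placebo". The same section drops the earlier table of crude frequencies of subjects with an event in favour of these estimates. SAP 6.2.2.2 carries the approach over: "The supportive analyses of the secondary time-to-event endpoints will correspond to those done for the primary composite endpoint in the FAS and PPS".

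Competing deaths are censored throughout:

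- **Primary composite.** SAP 6.2.1.1 censors at non-CV death, and SAP 6.2.1.2 keeps this in the sensitivity analyses: "Non-CV deaths will be treated as censored observations as in the primary analysis".
- **Renal composites.** SAP 6.2.2.1, for the window after the last complete visit: "In addition, should the subject have a non-renal death in this period then the date of death will be used as the censoring date".
- **All-cause hospitalization.** SAP 6.2.2.1: "Randomized subjects without a hospitalization event at the time of analysis will be censored at the date of their last contact", or at death. The recurrent-event mean cumulative function in SAP 6.2.2.2 follows the same rule.

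SAP 6.2.4 itself describes death from other causes as a competing event, to be handled by a while-alive strategy. SAP 6.4.1 and 6.4.2 use Aalen-Johansen estimates, with mortality as the competing risk, for hyperkalaemia events and for potassium above 5.5 or 6.0 mmol/L. No efficacy output does so.

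**The concern.** When competing deaths are censored, Kaplan-Meier redistributes those who died as if they could still have the event later. One minus Kaplan-Meier is then the risk in a hypothetical population where nobody dies of the other causes. It is not the proportion of patients who will have the event, which is what a cumulative incidence and an NNT are read as. It is always the larger of the two when competing deaths occur.

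Two features of this SAP make the point more than terminology. First, benefit would be shown on the hypothetical scale and hyperkalaemia on the actual scale, so an NNT could not properly be set against the hyperkalaemia risk. Second, CV death, a component of the trial's primary endpoint, is itself a competing event for the renal composites, so equal competing mortality in the two arms cannot be taken for granted there.

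The Greenwood variance belongs to the Kaplan-Meier estimate and does not carry over to the correct one. A mean cumulative function censored at death has the same fault: it estimates the mean number of hospitalizations as if no one died.

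**Working it through.** **A figure to reproduce.** The documents state no cumulative incidence, NNT or competing-death rate. The nearest figure is in protocol 10.4: 970 to 976 events and 6212 to 6286 subjects for 90% power. A Markov (Lakatos) log-rank model with 8% placebo events, 0.7% loss to follow-up and 5% finerenone discontinuation per year, with discontinuers returning to the placebo hazard, gives 972 events and 6234 subjects (44 months) and 979 and 6309 (48 months). These are within 0.4% of the stated values, so the planning inputs are read correctly.

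**Inputs.** From protocol 10.4: placebo event rate l = 0.08/yr, used here as a hazard, and HR 0.80, so l = 0.064/yr on finerenone. Assumed: competing-death hazard m = 1–4%/yr, equal in both arms unless stated, and constant hazards. Times: 4 years (the 48-month plan) and 3 years (the last time point listed in protocol 10.3.3.2).

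**Formulas.**

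- One minus Kaplan-Meier: KM = 1 − exp(−l·t)
- Aalen-Johansen: AJ = l/(l+m) · (1 − exp(−(l+m)·t))
- NNT = 1/(placebo risk − finerenone risk)

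**Worked case, t = 4, m = 0.02.**

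- KM placebo: 1 − exp(−0.32) = 0.2739. KM finerenone: 1 − exp(−0.256) = 0.2259. Difference 0.0480, NNT 20.8.
- AJ placebo: 0.08/0.10 × (1 − exp(−0.40)) = 0.2637. AJ finerenone: 0.064/0.084 × (1 − exp(−0.336)) = 0.2174. Difference 0.0463, NNT 21.6.

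**Primary endpoint, equal competing mortality.**

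| t (years) | m (/yr) | KM placebo | AJ placebo | KM too high by (relative) | NNT KM | NNT AJ |
|---|---|---|---|---|---|---|
| 4 | 0.01 | 27.4% | 26.9% | 1.9% | 20.84 | 21.21 |
| 4 | 0.02 | 27.4% | 26.4% | 3.8% | 20.84 | 21.59 |
| 4 | 0.03 | 27.4% | 25.9% | 5.8% | 20.84 | 21.98 |
| 4 | 0.04 | 27.4% | 25.4% | 7.7% | 20.84 | 22.36 |
| 3 | 0.01 | 21.3% | 21.0% | 1.4% | 25.85 | 26.21 |
| 3 | 0.02 | 21.3% | 20.7% | 2.9% | 25.85 | 26.58 |

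Reading the 8% as an annual proportion instead (hazard −ln 0.92 = 0.0834) gives a 4-year NNT of 20.2 against 21.0 at m = 0.02. The gap is about the same.

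**Unequal competing mortality** (placebo m = 0.02, t = 4). The correct NNT is 22.4, 21.6, 20.9 and 20.5 at finerenone/placebo death ratios of 0.8, 1.0, 1.2 and 1.3, against 20.8 from Kaplan-Meier. The two agree at a ratio of about 1.2, and beyond it Kaplan-Meier understates the benefit.

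**Other endpoints, t = 4.**

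- Hospitalization at an assumed 0.25/yr, HR 0.80 and 3%/yr death: 63.2% against 60.2%, NNT 12.3 against 12.7, with reversal at a ratio of about 1.1.
- At m = 0.03 the relative overstatement is 6.0%, 5.8% and 5.1% for l = 0.03, 0.08 and 0.25. It therefore depends mainly on m·t and little on the event rate.
- Mean number of hospitalizations at a constant rate: the death-censored mean divided by the mean with death as terminal is m·t/(1 − exp(−m·t)), which is 1.020 at m = 0.01 and 1.082 at m = 0.04. The overstatement is 2.0–8.2%.

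**The case against.** The strongest reply is that this hardly matters. No test, hierarchy or stopping rule uses these outputs, and the error is small beside sampling error. Take 3700 per arm (half of the roughly 7400 in SAP section 3) with complete follow-up. At 3 years the Kaplan-Meier risk difference is 0.0387 with standard error 0.0092, so the 95% interval for NNT runs from about 18 to 48. At m = 0.02 the bias in the difference is 0.0387 − 0.0376 = 0.0011, about 0.11 standard errors. At 4 years with m = 0.04 it is about 0.33 standard errors. That stands, and it is why the point is modest. It does not make the estimator right: the bias is systematic and is not covered by the confidence interval.

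The size rests on assumed death rates, and the planning values may not hold. Protocol 10.4 expects an observed HR closer to 1, and SAP section 3 reports slower events than assumed. At an assumed 0.05/yr and m = 0.02 the 4-year placebo gap falls from 1.0 to 0.7 percentage points, although the relative error stays near 4%. The NNT direction is not certain either; only the overstatement in each arm is.

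The SAP also reports rates per 100 patient-years, all-cause mortality and time to non-CV, non-renal death, so competing mortality would be visible. None of these yields a correct risk or NNT.

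Finally, for the renal composites a non-renal death sets the censoring date only within five months of the last complete visit, so it may seem that a new rule is needed. It is not: deaths that the present rules use as the censoring date become competing events, and all other censoring, including the 30-day limits in the PPS and on-treatment analyses, stays as it is.

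**Conclusion.** The concern holds. As written, the SAP will report efficacy risks labelled as cumulative incidence that are biased upward in each arm, and an NNT derived from them. For the primary endpoint at the planning values, the placebo risk is overstated by 1.9–7.7% (relative) at 4 years for competing mortality of 1–4%/yr, and NNT is 1.8–6.8% too low if that mortality is equal in the arms. The competing-death rates, the hospitalization rate and constant hazards are assumptions; the upward direction within each arm depends on none of them. The NNT direction does depend on the balance of competing deaths.

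The log-rank test, the Cox hazard ratio, all-cause mortality and the type I error rate are untouched. The change should be made, but the trial's confirmatory conclusion does not depend on it.

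**What to change.** - In SAP 6.2.1.2 and 6.2.2.2, derive cumulative incidence, its difference, the confidence interval and NNT from the Aalen-Johansen estimator, with its matching variance in place of Greenwood. The competing event is non-CV death for the primary endpoint, non-renal death for the renal composites and any death for hospitalization.
- For recurrent hospitalizations, use a mean function that treats death as terminal (Ghosh-Lin). This part can be decided separately from the first.
- Kaplan-Meier curves may stay, provided they are not labelled cumulative incidence in SAP 6.2.1.1 or 6.2.1.2.
- Leave the log-rank test and the Cox model as they are.

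The cost is SAP wording and some programming. Aalen-Johansen is already planned for safety, and protocol 13.1.2 has the event committee classify all deaths, so no new data are needed. Ghosh-Lin is new to the SAP and would need its own specification. Alpha and the primary test do not change. Reported absolute risks will fall and, if competing mortality is similar in the arms, the absolute benefit will look slightly smaller.

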6.2.2 Analysis of secondary efficacy variables

6.2.2.1 Secondary efficacy variables: primary analysis

Secondary efficacy variables are as follows:

- Time to first occurrence of the following renal composite endpoint:
 - onset of kidney failure, a sustained decrease of eGFR $\geq 40\%$ from baseline over at least 4 weeks, or renal death
- Time to all-cause hospitalization
- Time to all-cause mortality
- Change in UACR from baseline to Month 4
- Time to first occurrence of the following renal composite endpoint: onset of kidney failure, a sustained decrease in eGFR of $\geq 57\%$ from baseline over at least 4 weeks or renal death.

The primary analysis of the secondary efficacy variables will be conducted in the FAS.

See section 4.7 for the testing hierarchy for secondary endpoints and for multiplicity adjustment of significance levels.

The primary analysis of the secondary time-to-event endpoints will be conducted analogously to the primary analysis of the primary composite endpoint, with modifications to the

censoring rules as the events will differ. In the event of premature termination from the study with no subsequent follow-up information, subjects without any information about the composite endpoint after baseline will be censored at Day 1, and the following censoring rules will also apply:

- Renal events will be counted up to the day of the last visit when complete information on all components of the composite renal endpoint is available with an additional rule for events occurring after this visit. To account for events of kidney failure or renal death after the last eGFR is recorded at a clinic visit, such events will be included in the efficacy analysis if they occur in the period up to one day before the next planned clinic visit. This period would be a maximum of 5 months, given the next scheduled clinic visit should take place 4 months later, plus a time window for late attendance of one month. In addition, should the subject have a non-renal death in this period then the date of death will be used as the censoring date. Randomized subjects without an event of the renal composite endpoint at the time of analysis will be censored at the date of their last visit when complete information on all components of the composite renal endpoint is available, up to and including the EOS visit (should this visit satisfy this rule), or date of non-renal death using a time window of 5 months as above if a subsequent clinic visit had been planned.
- Hospitalization events will be counted up to the day of withdrawal from the study or death. Randomized subjects without a hospitalization event at the time of analysis will be censored at the date of their last contact up to and including the EOS visit or date of death.
- All-cause mortality will be counted up to the last date vital status could be obtained. Randomized subjects without such an event at the time of analysis will be censored at the last date vital status could be obtained up to and including the EOS visit.

An ANCOVA model will be fitted to the logarithmized ratios of UACR at Month 4 to UACR at baseline including the factors treatment group, the stratification factors region, type of albuminuria, eGFR category and history of CVD and the logarithmized baseline UACR as covariate. Corresponding two-sided 95% confidence intervals will be computed. As the baseline UACR defines the type of albuminuria, the log-transformed baseline UACR will be nested as covariate in type of albuminuria.

